**10. Statistical Analysis:**

Analysis of Data: A repeated measures design has four groups of ten subjects each for a total of forty subjects. Each subject is measured during the hypogonadal baseline, at the end of the two months of addback, and during the following month (i.e., continued addback in group 2 or withdrawal in group 1). The effect of hormonal addback and withdrawal in subjects and controls on mood and biological parameters will be calculated using ANOVA-R with post-hoc Bonferroni t-tests.

Sample Size Justification: Based on previous data (61), the between-subject standard deviation is 0.69 and the within-subject standard deviation is 0.28. This design achieves 67% power when an F test is used to test the Groups factor at a 5% significance level and the actual standard deviation among the appropriate means is 0.30 (an effect size of 0.43), achieves 81% power when an F test is used to test the Times factor at a 5% significance level and the actual standard deviation among the appropriate means is 0.16 (an effect size of 0.57), and achieves 60% power when an F test is used to test the group by time interaction at a 5% significance level and the actual standard deviation among the appropriate means is 0.13 (an effect size of 0.46).

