Despite these observations, there are only a few systematic studies of the role of gonadal steroids in the etiology of PPD. This probably reflects a number of factors, including the low prevalence of PPD in the community, the presence of numerous psychosocial and medical stressors during pregnancy and the puerperium, and the difficulties involved in recruiting and evaluating women who are either pregnant or lactating and nursing an offspring. To avoid these problems, we propose to study women with a history of PPD compared with women without a history of PPD, in order to answer the questions, 1) “Are women who develop PPD specifically susceptible to the hormonal events of pregnancy and the puerperium?”; and 2) Is it the abrupt withdrawal of gonadal steroids or the prolonged exposure to gonadal steroids that is associated with mood symptoms in these women?

Preliminary results of this study demonstrate that acute withdrawal of estradiol and progesterone is associated with a recurrence of mood and behavioral symptoms in women with a history of PPD but not in women lacking such history (61). These findings document a differential sensitivity to changes in gonadal steroid levels in women with a history of PPD, similar to what is seen in women with premenstrual syndrome. However the specific role of hormonal withdrawal is unclear as we observed that women with PPD were also significantly more symptomatic than controls during the addback phase of hormonal treatment (though less robustly than during the withdrawal phase). It is possible, therefore, that the duration of exposure to gonadal steroids rather than their withdrawal was the critical determinant of symptom precipitation; i.e., continued exposure to estradiol and progesterone replacement in our study might have been associated with equal levels of mood symptoms. Accordingly, we propose to mimic the hormonal events of pregnancy by randomly assigning patients and volunteers to either a withdrawal or continued replacement group (details in Clinical Assessment and Procedures). Furthermore, in order to establish PPD as a distinct phenotype, we will study a

group of women with histories of major depression occurring outside of the perinatal period to test whether the mood and HPA axis effect of this paradigm are specific to postpartum depression or a nonspecific response to any major depressive episode.

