## **2. Study Objectives:**

There are several lines of evidence suggesting a potential role for the hormonal events that occur during pregnancy and parturition in precipitating mood and behavioral changes in a subgroup of women:

- 1) Gonadal steroids modulate the activity of various neurotransmitter systems,
- 2) Gonadal steroids may be efficacious in the treatment of PPD;
- 3) Women with a history of PPD are vulnerable to the development of recurrent episodes of PPD during subsequent pregnancies.

In our previous findings in this protocol, the specific role of hormonal withdrawal was unclear as we observed that women with PPD were also significantly more symptomatic than controls during the addback phase of hormonal treatment. It is possible, therefore, that the duration of exposure to gonadal steroids rather than their withdrawal was the critical determinant of

symptom precipitation. Thus, in this current protocol, we propose to mimic the hormonal events of pregnancy and randomly assign patients and volunteers to either a withdrawal or continued replacement group. Furthermore, in order to establish PPD as a distinct phenotype, we will study a group of women with histories of major depression occurring outside of the perinatal period to test whether the mood and HPA axis effect of this paradigm are specific to postpartum depression or a nonspecific response to any major depressive episode.

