**3. Subjects:**

**a) Description of Study Populations:**

This study will enroll -40 asymptomatic women with a past postpartum depression, 20 asymptomatic women with a past major depression (not related to the postpartum), and 40 asymptomatic women with no past Axis I psychiatric illness.

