the minor depression module of the SADS-L. Urinary HCG will be determined to rule out pregnancy. Subjects who meet the inclusion criteria and who are medication free may be asked to return for follow-up interviews. During these interviews, phenomenological assessments may be performed by instruments such as the Premenstrual Tension Syndrome Scale (Steiner-Carroll Scale) (84), Beck Depression Inventory (85), Spielberger State-Trait Anxiety Inventory (86), Hamilton Rating Scales for Depression and Anxiety (87), Edinburgh Postnatal Depression Scale (88)) and related psychological measures. Additionally, subjects will be asked to fill out symptom self-rating scales, a modified version of the Daily Symptom Rating Form (Halbreich and Endicott) (89) and visual analogue scales (90), on a daily basis. During screening in protocol 81-M-0126 all subjects will receive a careful medical screening and will be excluded if there is evidence of significant renal, cardiac, hepatic, or other medical disorder. All patients will receive routine physical and laboratory examinations such as urinalysis, hematocrit, hemoglobin, BUN, creatinine, liver function tests, electrolytes, HIV, and a serum pregnancy test. Additionally, all women will have a normal EKG, and a normal PAP and gynecologic exam within the past year.

Subjects will be seen at the outpatient clinic on a regular biweekly basis. (Total = three baseline and 15 visits during treatment and follow-up.) During clinic visits, subjects will be monitored and managed for side effects, and blood samples will be drawn.

Research Procedures: Following the baseline period patients will receive 3.75 mg of the gonadotropin releasing hormone (GnRH) agonist leuprolide acetate (Lupron) during the early follicular phase of the menstrual cycle via intramuscular injection on a monthly basis in our clinic for five months. During the first two months of GnRH agonist administration, all subjects

will receive placebo progesterone and placebo estradiol tablets and will be told that at some point the placebo pills will be switched to active medication.

After the second month of Lupron-alone treatment, active estradiol and progesterone replacement will be initiated. Subjects shall be randomly assigned to one of two groups, and treatment shall be administered as follows:

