**b. Data and sample sharing plan**

This protocol is subject to the Genomic Data Sharing (GDS) policy. Data and samples will be shared with dbGaP, and The Perinatal Psychiatry Genetic Consortium - Postpartum depression: Action towards Causes and Treatment (PACT), which is headquartered at The University of North Carolina at Chapel Hill.

Data and samples may also be shared with collaborating laboratories at NIH or outside of NIH and/or submitted to NIH-designated repositories and databases if consent for sharing was obtained. Repositories receiving data and/or samples from this protocol may be open-access or restricted access.

Samples and data will be stripped of identifiers and may be coded (“de-identified”) or unlinked from an identifying code (“anonymized”). When coded data is shared, the key to the code will not be provided to collaborators, but will remain at NIH. Data and samples may be shared with investigators and institutions with an FWA or operating under the Declaration of Helsinki (DoH) and reported at the time of continuing review. Sharing with investigators without an FWA or not operating under the DoH will be submitted for prospective IRB approval. Submissions to NIH-sponsored or supported databases and repositories will be reported at the time of Continuing Review. Submission to non-NIH sponsored or supported databases and repositories will be submitted for prospective IRB approval.

Required approvals from the collaborating institution will be obtained and materials will be shipped in accordance with NIH and federal regulations.

The proposed research with our collaborators will be in accord with the purpose of the study stated in the consent that participants signed from the start of the protocol in 1995 to present. Starting in the 2008 consent forms, subjects were given the option whether they wanted to share their samples or not.

The ability to perform a meta-analysis of data will move the field forward. The plan is to focus on investigating the heterogeneity of Perinatal Depression (PND) in order to identify clinical subtypes.

Human tissue samples are being shared with collaborators of the PACT Consortium with a pending Material Transfer Agreement from the Office of Technology Transfer.

All personally identifiable information will be removed from the data and data will be coded with a research identifier that is not derived from or related to information about the subjects.

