**7. Risks and Discomforts:**

Potential discomforts in this study could arise from the medications administered in this study, the repeated venipuncture (i.e., bruising or pain at site of needle entry), the completion of rating scales, and the behavioral and endocrine challenge studies.

Medications: We do not expect any adverse side effects associated with the hormonal manipulations outlined in this protocol for the following reasons: First, we will be administering the physiologically relevant steroid hormones (estradiol and progesterone) and not the substituted steroids (such as ethinyl estradiol or norethindrone) present in many oral contraceptives and which have been reported to have a potentially more serious profile of side

effects. Second, the doses of Lupron, estradiol and progesterone, and the duration for which they will be administered in this protocol, will result in plasma hormone levels comparable to those commonly used for in vitro fertilization (IVF) protocols lasting 1-3 months. Therefore, based on current IVF procedures (80 ,94-96) ([name], personal communication) we do not anticipate any adverse incidents arising from the proposed doses of estradiol and progesterone. Third, no adverse reactions or events were encountered in the 25 women who completed the study to date. Finally, comparable extended, uninterrupted gonadal steroid treatment (such as oral contraceptives) for 6 to 12 weeks has been shown to be well-tolerated (97).

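### Section 10 plans and powers 40 women in four groups while Section 3 enrols 100 in three diagnostic groups; the major-depression aim has no contrast, and the stated powers of 67/81/60% do not reproduce

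*Combined protocol and SAP*

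**What the plan says.** Section 10 (Statistical Analysis) describes the design in one sentence: "A repeated measures design has four groups of ten subjects each for a total of forty subjects". Each woman is measured at three times: hypogonadal baseline, the end of two months of addback, and the following month. The analysis is a repeated-measures ANOVA in subjects and controls, with post-hoc Bonferroni t-tests. The sample-size paragraph gives a between-subject SD of 0.69 and a within-subject SD of 0.28. It claims 67% power for Groups, 81% for Times and 60% for group by time, each at the 5% level.

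Section 3a gives different numbers. Besides 40 women who have had PPD, the study is to enrol the following: "20 asymptomatic women with a past major depression (not related to the postpartum), and 40 asymptomatic women with no past Axis I psychiatric illness".

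Section 4 (Research Procedures) splits participants by arm: "Subjects shall be randomly assigned to one of two groups, and treatment shall be administered as follows". The arms are withdrawal and continued replacement.

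Section 1b says the study will include a "group of women with histories of major depression occurring outside of the perinatal period", and Section 2 gives the reason, which is to "test whether the mood and HPA axis effect of this paradigm are specific to postpartum depression".

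The protocol also has a history. Section 2 says "In our previous findings in this protocol, the specific role of hormonal withdrawal was unclear". Section 5b refers to the purpose "stated in the consent that participants signed from the start of the protocol in 1995 to present". Section 7 reports that "no adverse reactions or events were encountered in the 25 women who completed the study to date", and Section 8 mentions observations on 16 participants.

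**The concern.** A sample-size section should describe the study that will be run. Here a reader cannot tell how many women in each diagnosis-by-arm cell are to be randomised and analysed, or whether the power statement covers them. The number matters because the protocol deliberately provokes mood symptoms.

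The MDD group is there to answer one question, and the analysis section gives no means of answering it. Without a named contrast, specificity to PPD would be judged by whichever comparison is chosen afterwards, at unknown precision.

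The three powers are the only quantitative support for the sample size. If they do not follow from the design beside them, the reader cannot know what design, formula or inputs produced them.

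**Working it through.** **Numbers of women.** Section 10: 4 × 10 = 40. Section 3: 40 + 20 + 40 = 100. No dropout allowance, evaluable-sample rule or accrual history links the two.

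**Cells.** Three diagnoses by two arms make six cells. Section 10 has four, which two diagnoses by two arms would fill. Its text mentions only subjects and controls, and its generic post-hoc t-tests identify no PPD-versus-MDD comparison.

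**Effect sizes (Section 10 inputs).** The stated values reproduce, allowing for rounding:
- Groups: 0.30/0.69 = 0.435 (stated 0.43)
- Times: 0.16/0.28 = 0.571 (stated 0.57)
- Interaction: 0.13/0.28 = 0.464 (stated 0.46)

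**Powers.** Non-central F, alpha 0.05, N = 40, three times, sphericity assumed, non-centrality λ = N × f²:
- Groups: λ = 40 × 0.435² = 7.56
- Times: λ = 40 × 0.571² = 13.06
- Interaction: λ = 40 × 0.464² = 8.62

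With four Groups levels the degrees of freedom are (3, 36), (2, 72) and (6, 72). With two levels they are (1, 38), (2, 76) and (2, 76).

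| Test | Stated | Four-level Groups | Two-level Groups |
|---|---|---|---|
| Groups | 67% | 57.5% | 76% |
| Times | 81% | 89.7% | 90% |
| Interaction | 60% | 52.5% | 73% |

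Neither column gives the stated trio.

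**Times against interaction, four levels.** Both tests use the same N and the same error SD (0.28), so any common scaling of λ cancels. Power of 81% for Times needs λ = 10.29. The interaction then has λ = 10.29 × (0.464/0.571)² = 6.79, which gives 42%. With a Greenhouse-Geisser epsilon of 0.5, the minimum for three times, it is 44%. Taking the Times power as 81.5% and the SDs of means at their rounding limits (0.155 and 0.135) raises this to at most 51%. In reverse, 60% for the interaction implies 92–94% for Times. A sphericity correction does not close the gap: with λ = N × f², epsilon 0.72 brings Times to 81% but takes the interaction to 43%.

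**The same check, two levels.** Power of 81% for Times now implies 62–64% for the interaction, which is compatible with the stated 60% once rounding is allowed for. At epsilon 0.72 the formula gives 81% and 63%. Groups power, which epsilon does not affect, stays at 76% rather than 67%.

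**Sensitivity to the formula.** With four levels, 0.69 read as a random-intercept SD and 0.28 as the residual SD, the powers are 55.0%, above 99.9% and 97.3%. This misses the stated figures again, with Times and interaction far above them.

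**If the Section 3 numbers are randomised.** The plan gives no allocation ratio. Assuming 1:1, PPD and control women form four cells of 20 (N = 80), and λ = N × f² gives 90%, above 99% and 88%.

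**The case against.** The strongest defence of the numbers is that Section 3 may be cumulative. The protocol dates from 1995, reports earlier findings and counts earlier completers, so 40 could be the current randomised stage and 100 the total over the protocol's life. That is plausible and cannot be excluded. A reader might infer that 60 more women will be exposed without a rationale, but the documents support this only if Section 3 is the target for the randomised stage. What stands is that the plan does not say which it is.

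On the powers, the Groups factor may have been meant as two-level, since Section 10 does not state its degrees of freedom. That objection succeeds against any claim that 81% and 60% are incompatible under every convention: with a two-level factor they are compatible. It does not rescue all three figures, because Groups is then 76% under the same formula. Four levels is also the more literal reading of the design sentence.

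On the MDD group, it is tempting to say that its contrast must be less precise. With assumed cells of 20/20 for PPD and controls and 10/10 for MDD, the standard error of PPD-versus-MDD by arm is √[(2/20 + 2/10)/(4/20)] = 1.22 times that of PPD-versus-control by arm. With equal cells the ratio is 1.00. No cell sizes are stated, so the ratio illustrates the question and does not measure a defect.

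**Conclusion.** Two parts rest on the text alone: 40 and 100 are not reconciled, and the PPD-versus-MDD aim has no cell, named contrast, power or precision in Section 10.

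The third part is arithmetic. The stated 67/81/60% does not reproduce for 40 women at three times. Under λ = N × f² with sphericity, the stated figures miss by 7 to 10 percentage points with a four-level Groups factor and by 9 to 14 points with two levels. The mutual conflict between the Times and interaction figures holds only with four levels.

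A reader might conclude that the study is underpowered, or that true Groups power is lower than claimed. The documents do not support either. The direction of each error depends on the factor degrees of freedom, the formula and the covariance convention, none of which is stated. If about 80 PPD and control women are randomised, power for that comparison is understated rather than short. The supported conclusion is that the sample-size section does not identify the design it supports and its powers cannot be relied on as written.

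**What to change.** - State the number of women in each diagnosis-by-arm cell to be randomised and analysed under the current design, and whether Section 3 counts earlier participants.
- Include the MDD group in the repeated-measures model, and pre-specify a PPD-versus-MDD by arm (by time) contrast alongside PPD-versus-control.
- Replace 67/81/60% with powers recomputed for the actual cells, stating one formula, the degrees of freedom of each factor, the covariance or sphericity assumption, and the outcome scale to which 0.69 and 0.28 refer.
- Give the power or precision of the MDD contrast at its actual cell sizes.

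The cost is a recalculation and a change of wording, with no extra patients. Some stated figures may become less favourable, and the MDD contrast may prove less precise than PPD-versus-control.

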Group 1 (“withdrawal” group) - while continuing to receive monthly Lupron injections, all women in this group will be started on 2 mg B.I.D. of 17 beta-estradiol and 200 mg B.I.D. of progesterone for a period of eight weeks. After four months of GnRH agonist with placebo (two months) and estradiol/ progesterone replacement (two months), placebo will be substituted for the active medication while subjects continue on Lupron for another month. Participants will then be followed for an additional two months while unmedicated. Total duration of treatment with Lupron shall be five months.

Group 2 (“continued replacement” group) - while continuing to receive monthly Lupron injections, all women in this group will be started on 2 mg B.I.D. of 17 beta-estradiol and 200 mg B.I.D. of progesterone for a period of 12 weeks. Subjects shall receive Lupron for a total of five months, with placebo (two months) and estradiol/ progesterone replacement (three months). Participants will then be followed for an additional two months while unmedicated. Total duration of treatment with Lupron shall be five months.

The difference between these groups is, therefore, the duration of treatment with estradiol and progesterone - eight weeks of hormonal addback in the withdrawal group and 12 weeks of hormonal addback in the continued addback group. The fifth month of Lupron, then, provides the comparison between the effects of hormonal withdrawal and hormone continuation.

During the active medication phase of the trial, blood levels of progesterone and estradiol will be determined and the doses will be titrated accordingly by an unblind co-investigator. The

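### No PPD-versus-control contrast pooled over arms is specified for the addback phase; diagnosis and arm sit in one four-level Groups factor and the post-hoc t-tests are undefined

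*Combined protocol and SAP*

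**What the plan says.** Section 10 (Statistical Analysis) describes the design thus: "A repeated measures design has four groups of ten subjects each for a total of forty subjects". On timing it says "Each subject is measured during the hypogonadal baseline, at the end of the two months of addback, and during the following month", and effects on mood and biological measures "will be calculated using ANOVA-R with post-hoc Bonferroni t-tests". The sample-size paragraph treats the cells as one factor: the design "achieves 67% power when an F test is used to test the Groups factor at a 5% significance level", with further figures for Times and for group by time. The SDs are given as "the between-subject standard deviation is 0.69 and the within-subject standard deviation is 0.28". Diagnosis and arm do not appear as separate factors. No contrast is named, and the text does not say which pairs the t-tests compare, how many there are, whether they are paired, or whether they use scores or changes.

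Section 4 (Study Procedures) starts both randomised arms on the same estradiol and progesterone regimen and separates them only after eight weeks: "The difference between these groups is, therefore, the duration of treatment with estradiol and progesterone". It assigns the comparison of withdrawal with continuation to the fifth month of Lupron.

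Section 1.b asks first whether women who develop PPD are specifically susceptible to these hormonal events. It reports that in the earlier data "women with PPD were also significantly more symptomatic than controls during the addback phase of hormonal treatment". Section 2 repeats this as the reason for adding the randomisation.

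**The concern.** The addback difference between women with PPD and controls is the observation that made the role of withdrawal unclear, so this trial needs to estimate it cleanly. At the end of eight weeks the two arms of each diagnosis have had the same planned treatment. For that visit the design has two groups of 20, not four of 10.

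As written, the addback question has no term of its own. It is one part of a 6-df interaction that also responds to what happens in month 5. After a significant interaction, the reader depends on follow-up tests that the plan leaves open and that, if run between cells, would use ten women a side. At stake are power for the first stated question and, more importantly, the ability to say whether a significant result reflects exposure or withdrawal.

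**Working it through.** **Inputs.** From Section 10: four groups of 10, three visits, between-subject SD 0.69, within-subject SD 0.28, two-sided 5%. Assumed, because the documents give no value: the true PPD-control difference d in change from baseline to end of addback, taken as 0.26 to 0.50; six Bonferroni pairs (all pairs of four cells); and 0.28 as the residual SD of one measurement, equal and independent across visits.

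**The plan's own power figures.** Noncentral F with λ = N f², N = 40:
- Groups: f = 0.30/0.69 = 0.435, λ = 7.56, df 3 and 36: 57.5% (stated 67%)
- Times: f = 0.16/0.28 = 0.571, λ = 13.06, df 2 and 72: 89.7% (stated 81%)
- Group by time: f = 0.13/0.28 = 0.464, λ = 8.62, df 6 and 72: 52.5% (stated 60%)

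The stated figures do not reproduce for four groups of 10. That is a separate matter; only the SDs are carried forward here.

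**Pooled contrast, 20 v 20 on change.** SD of change = 0.28 × √2 = 0.396. SE = 0.396 × √(2/20) = 0.125. At d = 0.40 the noncentrality is 0.40/0.125 = 3.19 on 38 df, giving 88%. At a level of 0.05/6 it is 66%; at 0.05/2 it is 80%.

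**Planned 6-df test.** Let both PPD cells rise by d at the two later visits. The diagnosis difference over visits is (0, d, d); centred it is (−2d/3, d/3, d/3), with sum of squares 2d²/3. Each of the four cells lies half of this from the mean, so the total is 4 × ¼ × 2d²/3 = 2d²/3. Then λ = 10 × (2/3) × 0.16/0.0784 = 13.6 at d = 0.40, and power on 6 and 72 df is 76%. An effect confined to the addback visit, (0, d, 0), gives the same λ. One that half persists, (0, d, d/2), has sum of squares d²/2, λ = 10.2, and so lower power.

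**Cell-level follow-up on change, 10 v 10.** SE = 0.396 × √(2/10) = 0.177. At d = 0.40 the noncentrality is 2.26 on 18 df: 57%, or 28% at 0.05/6.

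| Assumed d | Pooled change, 20 v 20, 5% | 6-df group by time, 5% | Change, 10 v 10, 5% | Change, 10 v 10, 0.05/6 |
|---|---|---|---|---|
| 0.26 | 53% | 35% | 28% | 10% |
| 0.30 | 65% | 47% | 36% | 14% |
| 0.40 | 88% | 76% | 57% | 28% |
| 0.50 | 97% | 93% | 76% | 47% |

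**Does a significant interaction answer the addback question?** Suppose there is no addback effect and only the PPD withdrawal cell rises, by 0.50, in month 5. The centred sum of squares is 3/4 over cells and 2/3 over visits, so λ = 10 × 0.25 × 0.75 × (2/3)/0.0784 = 15.9. The 6-df test is then significant 83% of the time. It cannot separate this case from a true addback difference.

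**Section 3 sizes.** If the 40 PPD women and 40 controls listed there are analysed (20 per cell), d = 0.30 gives 92% for the pooled contrast (40 v 40) and 83% for the 6-df test. Cell-level change scores give 65%, or 36% after Bonferroni for six pairs.

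**The case against.** A reader might infer that the plan ignores each woman's own baseline. It does not: the hypogonadal baseline is a level of the Times factor, and the group-by-time test is a within-woman test on all 40 women. A reader might also infer that the follow-up t-tests are unpaired comparisons of raw scores between cells of ten. Section 10 does not say so; they could be paired tests against baseline within a group, or could use the ANOVA error term. Both stronger readings should be left aside.

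The merged factor is itself partly a reading. Groups, Times and their interaction appear as factors only in the power paragraph. The analysis sentence speaks of addback and withdrawal in subjects and controls, which does not rule out a diagnosis term, and the four groups are never labelled.

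It can also be said that setting the pooled contrast at 5% beside corrected follow-up tests is unequal treatment. That is fair. At 0.05/6 the pooled contrast has 66% at d = 0.40, less than the omnibus test at 5%. The power gain over the omnibus test therefore depends on pre-stating the contrast rather than treating it as one of six. At the same corrected level, however, 66% still compares with 28% for the cell-level change comparison.

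What remains is that no diagnosis contrast pooled over arms is specified, the follow-up tests are undefined, and the omnibus test cannot attribute an effect to addback.

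**Conclusion.** The point holds as a gap in the analysis specification. For the addback question the plan relies on a 6-df test that is less efficient than one pre-stated contrast (76% against 88% at an assumed 0.40; 35% to 93% against 53% to 97% over 0.26 to 0.50). That test would also be significant 83% of the time from a month-5 withdrawal effect of 0.50 alone. If the undefined follow-up tests compare cells of ten, even on change scores, power at 0.40 is 57%, or 28% after correction for six pairs.

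These figures rest on the natural reading of the four groups as PPD or control by arm, on Section 10's within-subject SD, on assumed differences, and on an addback effect that either fully persists into month 5 or is confined to the addback visit. The loss against the omnibus test is moderate; the inability to attribute a significant result to addback is the stronger reason to change the plan.

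**What to change.** Replace the four-level factor in Section 10 with diagnosis by arm by time, and state:
- **Addback:** diagnosis by (end of addback minus hypogonadal baseline), pooled over arms, as a single 1-df PPD-versus-control contrast using within-woman error, or as an ANCOVA on the baseline value.
- **Month 5:** arm enters only at this measurement, with diagnosis by arm as a separate pre-stated contrast.
- **Past-MDD group:** if the 20 women with past non-postpartum major depression in Section 3 are analysed, include them as a level of diagnosis, with their comparison named.
- **Follow-up tests:** say which pairs, how many, whether paired, and on what scale.

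The cost is SAP wording, with the same visits and data. The contrasts must be fixed in advance and multiplicity across the addback and month-5 contrasts stated. If the 5% were split equally between those two, the addback contrast would have 80% rather than 88% at d = 0.40.
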